8.2 Multiplicity Adjustment

Not applicable.

9 Data handling Procedures

9.1 Handling Missing/Incomplete Data

9.1.1 Missing Data in Efficacy Analysis

Missing data will not be imputed for efficacy endpoints analyses.

9.1.2 Missing Data in Safety Analysis

Missing data will not be imputed for safety endpoints analyses.

9.2 Partial Dates

Partial dates may be imputed for medications to determine whether they are concomitant medications using the algorithm given below.

End dates will be imputed as follows:

- If marked “ongoing” with no end date, then this will be considered as concomitant medication.
- If only year is present, then impute date and month as 31-DEC.
- If month and year are present, then impute date with last date of the month.
- If date and year are present, then impute month as DEC.
- If year is missing, then impute subject’s last visit date in the study.

If the imputed end date is later than subject’s last visit date, then the subject’s last visit date will be used.

- In case the end date is partial, and we know that the medication has started after the last VR session, then the medication will not be considered as a concomitant medication.

In case of ambiguity, the worst case is considered (that is, concomitant medication) for safety analyses.

Example,

Partial End Date	Imputed End Date
--JUN2019	30JUN2019
-----2019	31DEC2019
12---2018	12DEC2018
14MAR----	Subject's last visit date

Imputed dates will be used for analyses and collected dates will be recorded in database will be displayed in listings.

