### **15.3.3. Important Protocol Deviations**

Important protocol deviations (IPDs) will be identified and documented based on a review of potential IPDs prior to database lock. The potential IPDs will be identified through programmatic checks of study data , as well as through review of selected data listings. The potential IPDs to be reviewed include, but are not limited to, subjects who:

- Did not meet inclusion/exclusion criteria.
- Did not properly use BVR-100 or BES-100.
- Received any disallowed concomitant medication.

Individual IPDs will be presented in a data listing. The number and percentage of subjects with IPDs will be summarized by type of deviation and treatment group.

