### **15.4.1. Concomitant Medications**

All medications will be coded to indication-specific ATC (Anatomical Therapeutic Chemical) classification (ie, ATC level 3) and preferred name using the World Health Organization Drug Dictionary (WHO-DD) Enhanced extended with WHODrug Global.

Any medications taken during the course of the study, with a start date on or after the date of the first use of BVR-100/BES-100 and with a start date prior to, and an end date on or after, the date of the first use of BVR-100/BES-100 will be considered concomitant medications. Medications that ended prior to the date of the first use of BVR-100/BES-100 will be considered prior medications. Prior and Concomitant medications will be summarized for the number and percentage of subjects using each medication by dosage form and overall by the drug class and preferred name for the safety population.

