11.14 Prior and Concomitant Medications

If a medication ended prior to first use of BVR-100/BES-100, then it is considered as prior medication.

If the medication ended on or after the first use of BVR-100/BES-100 or is ongoing, it is considered as concomitant medication.

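### SAP 9.2 removes a medication begun after the final VR session from the concomitant class only when its end date is incomplete, which conflicts with SAP 11.14 and leaves the drug out of both medication summary tables

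*SAP*

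**What the plan says.** SAP 9.2 gives rules for imputing incomplete medication end dates so that concomitant status can be decided. Three of its statements matter here.

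- The exclusion. Its condition is "In case the end date is partial, and we know that the medication has started after the last VR session", and its result is that "the medication will not be considered as a concomitant medication".
- The rule for a drug marked as ongoing "with no end date, then this will be considered as concomitant medication". This has no condition on when the drug began.
- The tie-break: "In case of ambiguity, the worst case is considered (that is, concomitant medication) for safety analyses".

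SAP 11.14 defines the two classes. For the first, "If a medication ended prior to first use of BVR-100/BES-100, then it is considered as prior medication". For the second, "If the medication ended on or after the first use of BVR-100/BES-100 or is ongoing, it is considered as concomitant medication". Neither definition has a cut-off at the final VR session.

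Protocol 15.4.1 counts as concomitant "Any medications taken during the course of the study, with a start date on or after the date of the first use of BVR-100/BES-100", and also drugs begun earlier that were still in use at or after first use. For a drug begun after first use, the end date plays no part.

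SAP 12.5 summarises prior and concomitant medications separately, with no third class, and lists all medications. SAP section 13, which records changes from the protocol, does not mention the 9.2 exclusion.

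**The concern.** Whether a drug is concomitant should depend on when it was taken, not on how completely its stop date was recorded. Under 9.2 and 11.14 together, two subjects who begin the same drug on the same day after their final session are classified differently if one has a full stop date and the other lacks the day. The second subject's drug then has no place in either summary table.

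What is at stake is the completeness of the on-study medication summary near the end of follow-up. Protocol 10.3 collects new medications until the end of study, and SAP 11.15 summarises adverse events until the end of study. An event that occurs after the final session is therefore counted, while a drug given for it can be missing from the concomitant table. A programmer also has to choose between two conflicting SAP rules.

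**Working it through.** This is a classification rule, so no power or sample-size formula applies. The check sets the rules side by side and follows one drug through them.

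**1. Reproduce the plan's own examples.** The 9.2 imputation rules, coded as written, return all four of the SAP's worked results: 30JUN2019, 31DEC2019, 12DEC2018, and the last visit date when the year is missing.

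**2. Illustrative subject (assumed dates).** First VR session 01OCT2023 (Day 1), final session 22NOV2023 (Day 53), drug begun 23NOV2023 (Day 54), last visit 25NOV2023 (Day 56).

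| End date as recorded | Imputed end, capped at last visit | SAP 9.2 with the exclusion | 11.14 alone | Protocol 15.4.1 |
|---|---|---|---|---|
| 25NOV2023 (complete) | not needed | concomitant (exclusion not triggered) | concomitant | concomitant |
| Month and year only | 30NOV2023, capped to 25NOV2023 | not concomitant | concomitant | concomitant |
| Year only | 31DEC2023, capped to 25NOV2023 | not concomitant | concomitant | concomitant |
| Year missing | 25NOV2023 | not concomitant | concomitant | concomitant |
| Ongoing | not needed | concomitant | concomitant | concomitant |

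The three incomplete formats are the only ones excluded. With the exclusion removed, all five rows are concomitant.

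**3. Can the excluded drug be prior?** No. Its end is no earlier than its start, its start is after the final session, and the final session is not before first use. The end therefore cannot precede first use, as the prior class requires.

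**4. Does the tie-break rescue it?** No. The exclusion operates only when the late start is known. By step 3 the missing part of the end date cannot alter the drug's status, so there is no ambiguity to resolve.

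**5. Where the drug still appears.** Listing 16.2.4.3 shows all medications (SAP 12.5). Table 14.1.6.3 counts psychotropics taken in the 12 hours before a visit and does not depend on concomitant status (SAP 12.6). The loss is therefore from Tables 14.1.6.1 and 14.1.6.2.

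**6. Length of the window.** It runs from the final session to the last visit.

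- Completer: Week 8 is Days 50 to 56, and the required sessions precede the closing telehealth visit, held in the last 3 days of that week (protocol 11.5.4). With all three sessions on Day 50, the maximum is 56 − 50 = 6 days. At one session a day, the pattern used as an illustration in SAP 11.17.5, the third session falls no earlier than Day 52, so the maximum is 56 − 52 = 4 days.
- Early termination: the visit should fall within 5 days of last exposure (protocol 11.5.6, SAP 11.6).
- Subject who stops sessions but stays in the study: longer. The extreme case, a final session on Day 7 and a visit on Day 56, gives 56 − 7 = 49 days.

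**The case against.** The strongest defence is that the bullet is a deliberate end-of-treatment cut-off which 11.14 fails to repeat. The documents do not show which section is the slip, so that intention cannot be ruled out. But the bullet as written does not act as a cut-off, because it spares drugs with complete end dates and ongoing drugs that began on the same day.

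A second defence is that the SAP takes precedence over the protocol's statistical section (SAP section 2). That stands, and it reduces the weight of the conflict with protocol 15.4.1. It does not settle 9.2 against 11.14, since both are SAP text.

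Third, triggering records should be rare. The drug must begin after the final session, must have stopped already, and must lack part of its stop date, although protocol 10.3 requires start and stop dates and times. This also stands.

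Three stronger readings are tempting, and the documents do not support them.

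- A reader might infer that these drugs vanish from the report. They remain in the full listing, and some psychotropics may remain in Table 14.1.6.3.
- A reader might infer that a prohibited drug would escape the important-deviation review, since protocol 15.3.3 names subjects who "Received any disallowed concomitant medication". That review uses programmed checks of study data together with review of selected listings. Nothing says that it uses the 9.2 classification, and SAP 9.3 places deviation review outside the SAP.
- A reader might take the seven-week window as typical. It needs a subject who stops every session after Week 1 yet attends to Week 8, despite the weekly reminders and direct contact in protocol 11.5.4.

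**Conclusion.** The inconsistency is real and minor. SAP 9.2 makes classification depend on date completeness, contradicts SAP 11.14, and leaves the affected drug outside both classes that SAP 12.5 summarises.

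The size is limited to two descriptive tables and probably to few records; the documents give no count. No efficacy analysis in SAP 12.8 or 12.9 uses medication status, so the CEQ, retention, time-on-task and LSAS results do not change. A reader might infer that the rule biases later symptom scores. It does not enter those analyses, and anyone interpreting the scores still has the full listing.

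The conclusion rests on reading 9.2 and 11.14 as written. The dates in the worked case are assumed, but the result holds for any drug begun after the final session.

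**What to change.** Delete the 9.2 bullet, so that 11.14 decides status however complete the end date is. If it helps the reader, mark drugs begun after the final VR session with a flag inside the concomitant table.

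If the sponsor did intend a post-treatment cut-off, state it in both 9.2 and 11.14, apply it equally to complete, partial and ongoing records, and summarise those drugs as a separate category so that none is left untabulated. Record the cut-off in SAP section 13 as a change from protocol 15.4.1.

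The first option costs one deleted SAP bullet and about one line of code. The second needs a few more lines of SAP text and one extra summary category. Neither needs new data.

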9.3 Clean File / Blinded Review Meeting

Pre database lock blinded data review and protocol deviation review is out of scope for this SAP. Sumitomo statistician will be part of these review and meetings.

10 Analysis Populations

The membership of the analysis populations will be reviewed and finalized prior to database lock with blinded data.

10.1 Enrolled Population

Enrolled Population includes all subjects who sign the informed consent form and are successfully screened.

The Enrolled Population will be used for summaries of subject disposition.

10.2 Full Analysis Set (FAS)

The Full Analysis Set (FAS) consists of all subjects enrolled and randomized into the study.

The FAS population will be used for summaries of subject disposition, demographic and baseline characteristics. Subjects will be analyzed according to the treatment group they were assigned at randomization.

10.3 Safety Population

The safety population consists of all randomized subjects who have completed at least one VR session.

The safety population will be used for the analysis of safety. Subjects will be analyzed as treated, regardless of the randomized treatment assigned, if this differs from that to which the subject was randomized.

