## 12. SAFETY REPORTING

### 12.1. Definitions

#### 12.1.1. Adverse Events

An adverse event (AE) is any untoward medical occurrence associated with the use of an investigational intervention in humans, whether or not considered related to the intervention.

Untoward medical occurrences that occur after the time of signing the Informed Consent Form (ICF) and prior to the first VR session are a subset of AEs referred to in analysis as pre-treatment events. Those that occur after first VR session are considered AEs. Importantly, all AEs, including pre-treatment events, are collected via the same form by investigator site staff, who will complete the AE form in the EDC, which will then immediately notify both the CRO and Sponsor.

An AE can, therefore, be any unfavorable and unintended sign (including an abnormal laboratory finding), symptom, or disease occurring after the administration of an investigational intervention, whether or not considered related to the investigational intervention. AEs may include the onset of new illness and the exacerbation of pre-existing conditions. AEs will be collected from after first use of the investigational intervention to the EOS/ET.

The Investigator should attempt to establish a diagnosis of the event based on signs, symptoms, and/or other clinical information. In such cases, the diagnosis should be documented as the AE and not the individual signs/symptoms.

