### 15.2. Analysis Populations

The effectiveness analyses will be based on the modified Intent-to-Treat (mITT) population, which includes all subjects who are randomized, have completed at least one VR session, and have a Baseline and at least one post-Baseline effectiveness measurement in CEQ. Additional analysis of the Per-Protocol (PP) population (defined as all subjects who have completed the 8-week intervention period without any important protocol deviations) is supportive, while the mITT population will be the primary analysis population. The primary effectiveness endpoint must achieve significance in the mITT to preserve type I error for the secondary endpoint.

The safety assessments will use the Safety population, which includes all subjects who are randomized and have completed at least one VR session.

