### **15.4.3. Safety Analyses**

Safety data including AEs, SAEs and, UADEs will be collected from the start date/time of Investigational Intervention, defined as the engagement with first intervention session, to the EOS/ET, and summarized by treatment group. Adverse events, AEs leading to discontinuation, serious AEs, and UADEs will be summarized by presenting, for each treatment group, the number and percentage of subjects with any AEs, and AEs by system organ class and preferred term. Adverse events will be further summarized by severity and by relationship to the Investigational Intervention.

AEs are defined as untoward medical occurrences that started at the same time of or after the first VR session. Untoward medical occurrences that started prior to the first VR session, but after signing the ICF are pre-treatment events.

Whenever available, the time information should be accounted for in the derivation of AEs vs. pre-treatment events. In the case where time is not available, untoward medical occurrences that started on or after the day of the first VR session will be considered AEs; those that started before the day of the first VR session, but after signing the ICF, will be considered pre-treatment events. The identification of AEs versus pre-treatment events will be determined programmatically, and not at the site level.

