10.4 Intent-to-Treat (ITT) Population

The Intent-to-Treat (ITT) population consists of all randomized subjects who have at least one VR session.

The ITT population is the primary population to analyze efficacy endpoints. Demographic and baseline characteristics of the ITT population will also be presented. Subjects will be analyzed according to the treatment they received.

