11.15 Adverse Events

Any Adverse Event (AE) is defined as any effect that occurs or worsens after the first VR session until EOS will be summarized. Any events that occur after the time of signing the Informed Consent Form (ICF) and prior to the first VR session are termed as pre-treatment events.

Related Adverse Events include Possibly, Probably and Definitely Related Adverse Events.

UADEs are serious adverse effects caused by, or associated with a device which were not previously anticipated to occur. UADEs collected in CRF data will be summarized.

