12.10 Safety Analyses

12.10.1 Adverse Events

All Adverse events will be coded using the MedDRA version 26.0 or Higher. All summaries will be summarized by treatment groups and total based on safety population. Total will not be displayed in the table.

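### The Safety population admits only subjects who finished a VR session, so an exposed subject who stops for an acute AE and never finishes one would be missing from every AE summary table

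*SAP*

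**What the plan says.** **Population.** SAP 10.3 states: "The safety population consists of all randomized subjects who have completed at least one VR session". Protocol 15.2 has the same condition: "The safety assessments will use the Safety population, which includes all subjects who are randomized and have completed at least one VR session". The synopsis repeats it. SAP 10.4 words the efficacy set without the completion condition: "The Intent-to-Treat (ITT) population consists of all randomized subjects who have at least one VR session". I find no statement in either document of when a session counts as completed.

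**Use of the population.** SAP 12.10.1 says of the AE tables: "All summaries will be summarized by treatment groups and total based on safety population". SAP 12.10.3 also takes its percentages from that set, and says that the total column will not be shown. SAP 12.10.2 lists all AEs by subject, and its text does not confine the listing to the Safety population. SAP 12.1 tabulates early terminations by reason on the FAS.

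**Timing of AEs.** SAP 11.15 says: "Any Adverse Event (AE) is defined as any effect that occurs or worsens after the first VR session until EOS will be summarized". It calls events between consent and that session pre-treatment. Protocol 12.1.1 has the same before/after split: "Those that occur after first VR session are considered AEs". Protocol 15.4.3 is wider. It dates the start of the intervention from engagement with the first session and says: "AEs are defined as untoward medical occurrences that started at the same time of or after the first VR session". Protocol 15.4.3.1 likewise counts from first use onward. If no clock time was recorded, protocol 15.4.3 works by day: "untoward medical occurrences that started on or after the day of the first VR session will be considered AEs".

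**Precedence.** SAP section 2 makes the SAP override the protocol's statistical section. SAP 13 lists no change to the Safety population or to the AE window.

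**The concern.** Completing a session happens after exposure and depends on how well the exposure is tolerated. Protocol 4.4 names motion sickness, dizziness, nausea and a possible panic attack among the risks, and says that a subject who is too uncomfortable can take the headset off. A subject who does so in session 1 and never finishes any later session has been exposed, but fails SAP 10.3. AE incidence is a safety endpoint, and the tables that report it would leave out the people who tolerated the device least. SAP 11.17.3 shows different session 1 content in the two arms, so the filter need not act equally on both.

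The timing wording is a smaller matter of the same kind. If the first session is taken as an interval, an event inside it is neither before nor after it. Protocol 15.4.3 says that the split between AEs and pre-treatment events is made programmatically, so the program will follow whichever wording governs.

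The pilot is meant to inform a registration RCT (protocol 4.3 and 7.3.1). These definitions would matter more if they were carried forward.

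**Working it through.** **1. The plan's own counts.** SAP 13 reports 52 subjects in the Safety population at the 19 January 2024 cut and says that ITT will include all 52. The difference is 52 − 52 = 0. This has two possible explanations:
- If the ITT wording means that a session was started, no subject at that cut had started without ever finishing one.
- If ITT was applied as a completed session, the two sets are the same by construction and the counts say nothing.

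**2. Population rule applied to one case.** Take a randomised subject who starts session 1, stops for an acute AE and never finishes a session.

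| Output | Source | Subject included? |
|---|---|---|
| AE summary tables | SAP 10.3, 12.10.1, 12.10.3 | No: in neither numerator nor denominator |
| AE listing | SAP 12.10.2 | Yes |
| Early termination by reason | SAP 12.1, on the FAS | Yes, if the subject leaves the study |
| ITT tables | SAP 10.4 | Yes if the wording means started; no if it means completed |

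**3. Size.** The documents give neither the number of such subjects nor the arm counts. Assume equal arms, 52/2 = 26, and one such subject added to one arm. A row with *a* subjects goes from *a*/26 to (*a* + 1)/27:
- *a* = 0: 0/26 = 0.0% becomes 1/27 = 3.7%.
- *a* = 2: 2/26 = 7.7% becomes 3/27 = 11.1%.

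With the planned 20 per arm, the subject would be one of the 20. A row with no other events then goes from 0/19 = 0.0% to 1/20 = 5.0%.

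**4. Timing rule applied to one event.** Suppose the first session runs from 10:00 to 10:15 and an event starts at 10:07.
- SAP 11.15, with the session read as an interval: not before 10:00, so not pre-treatment; not after 10:15, so not an AE. It is in neither class.
- Protocol 15.4.3 and 15.4.3.1: at or after 10:00, so an AE.
- SAP 11.15, with the session read as its start time: after 10:00, so an AE, and the gap closes.

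An event that worsens after the session counts under SAP 11.15 in any case. An event without a recorded time falls under the day rule of protocol 15.4.3. Only events with a clock time inside the first session are exposed to the ambiguity.

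**The case against.** The strongest reply is that nobody may be affected. The case needs a subject who starts, stops for an AE and then finishes none of the 24 required sessions. Protocol 11.5.3 has the support team ensure that session 1 is done on the baseline day, and 11.5.4 has it contact subjects who miss weekly content. The equal counts of 52 suggest that the ITT wording may be loose drafting for the same set. This stands as a limit on size. It does not repair the rule: follow-up makes such cases rarer but cannot make a subject who feels ill finish a session.

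A second reply is that the case is visible elsewhere. That is true. A reader might infer that such events vanish from the report, and the documents do not support that: the listing carries them, and the disposition table counts early termination with its reason. What is lost is the row by system organ class and preferred term, and its denominator.

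A third reply is that SAP 11.15 can sensibly be read as running from the start of the session. I accept that reading. Because the SAP overrides protocol 15.4.3, it should be written down, but it is an alignment note and not a second defect of equal weight.

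Two other stronger readings also fail. A change from 0/52 to 1/53 would not appear in the report, because the tables are by arm and the total is not displayed. Nor can one say what share of AEs falls in the first-session gap: session 1 is one of 24 required sessions, but the documents give no onset rate, and acute effects need not be spread evenly.

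**Conclusion.** The population point holds. As written, the rule drops exposed subjects who could not tolerate a session from all AE counts and percentages, and it disagrees with the protocol's own start of the safety window. The plan should be corrected.

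The documents do not show that any subject in this trial was affected, and the effect may be nil. The illustrative change of 3.7 percentage points in one arm's row assumes one such subject and equal arms of 26. The timing point holds only as an alignment of wording, and only for timed events inside the first session. CEQ and secondary endpoint conclusions are not affected.

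**What to change.** - **SAP 10.3:** define the Safety population as all randomised subjects who started at least one VR session, whether or not they finished it.
- **SAP 10.4:** use the same threshold wording, so that the two sets cannot be read differently.
- **SAP 13:** list the departure from protocol 15.2. The mITT population was replaced by ITT through the same section, so no protocol amendment is needed.
- **SAP 11.15:** count events that start or worsen at or after the start of the first VR session, and end the pre-treatment period at that time. This matches protocol 15.4.3 and 15.4.3.1. Protocol 12.1.1 can stay, because classification is programmatic and a protocol change would need sponsor and IRB/IEC approval (protocol 17.4).
- **Before database lock:** the sponsor should confirm that an aborted session leaves a start record. Protocol 10.2 says that use is recorded electronically, but 6.2 says that time-on-task is recorded after each session. If there is no such record, the SAP should name another source for the start.

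The cost is a few lines in the SAP and one data check. AE rates may rise slightly.
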